APPENDIX A. MAXIMUM ALLOWABLE BLOOD DRAW VOLUMES

This information is consistent with the National Institutes of Health (NIH) Pediatric Blood Volume for Research Guidelines (Howie 2011).

| PATIENT'S WEIGHT | | PATIENTS TOTAL VOLUME | MAXIMUM mL IN ONE BLOOD DRAW | |
|------------------|--------------|--------------------------|---------------------------------|--|
| Kg | lbs | mL | 2.5% of total blood volume | |
| 1 | 2.2 | 100 | 2.5 | |
| 2 | 4.4 | 200 | 5 | |
| 3 | 6.6 | 240 | 6 | |
| 4 | 8.8 | 320 | 8 | |
| 5 | 11 | 400 | 10 | |
| 6 | 13.2 | 480 | 12 | |
| 7 | 15.4 | 560 | 14 | |
| 8 | 17.6 | 640 | 16 | |
| 9 | 19.8 | 720 | 18 | |
| 10 | 22 | 800 | 20 | |
| 11 thru 15 | 24 thru 33 | 880-1200 | 22-30 | |
| 16 thru 20 | 35 thru 44 | 1280-1600 | 32-40 | |
| 21 thru 25 | 46 thru 55 | 1680-2000 | 42-50 | |
| 26 thru 30 | 57 thru 66 | 2080-2400 | 52-60 | |
| 31 thru 35 | 68 thru 77 | 2480-2800 | 62-70 | |
| 36 thru 40 | 79 thru 88 | 2880-3200 | 72-80 | |
| 41 thru 45 | 90 thru 99 | 3280-3600 | 82-90 | |
| 46 thru 50 | 101 thru 110 | 3680-4000 | 92-100 | |
| 51 thru 55 | 112 thru 121 | 4080-4400 | 102-110 | |
| 56 thru 60 | 123 thru 132 | 4480-4800 | 112-120 | |
| 61 thru 65 | 134 thru 143 | 4880-5200 | 122-130 | |
| 66 thru 70 | 145 thru 154 | 5280-5600 | 132-140 | |
| 71 thru 75 | 156 thru 165 | 5680-6000 | 142-150 | |
| 76 thru 80 | 167 thru 176 | 6080-6400 | 152-160 | |
| 81 thru 85 | 178 thru 187 | 6480-6800 | 162-170 | |
| 86 thru 90 | 189 thru 198 | 6880-7200 | 172-180 | |
| 91 thru 95 | 200 thru 209 | 7280-7600 | 182-190 | |
| 96 thru 100 | 211 thru 220 | 7680-8000 | 192-200 | |

Chart based on blood volume of:

1 to 2 kg 100 mL/kg (pre-term infant) >2 kg 80 mL/kg (term infant - adult)

Daily maximum: 3 mL/kg/day maximum. If doing more than one draw per day, be careful to not exceed the one time maximum OR the daily maximum 3.0 mL/kg per day.

The amount of blood that can be drawn in a 24-hour period is the same as the maximum amount column.

Patients admitted for a solid organ transplant (pre-transplant) are expected to exceed this volume. For all other patients, physician approval is required if maximum volume is to be exceeded for a one-time draw or daily maximum.

This information is similar to that used by the Committee on Clinical Investigations at Children's Hospital in Los Angeles, and at Baylor College of Medicine in Dallas, TX.

Adapted by Seattle Children's Hospital Laboratory April 2012, Seattle, WA.

Rev. 11/2018

APPENDIX B. STUDY DIARY: PATIENT PITOLISANT STUDY DRUG DOSING AND SLEEP DIARY

Appendix C. EXAMPLES OF STRONG CYP2D6 INHIBITORS, STRONG CYP3A4 INDUCERS, MEDICATIONS THAT PROLONG QT INTERVAL, AND CENTRALLY ACTING H₁ RECEPTOR ANTAGONISTS

| Medication Type | Examples | |
|--------------------------------------|---|--|
| Strong CYP2D6 inhibitors | paroxetine, fluoxetine, bupropion, quinidine, terbinafine | |
| Strong CYP3A4 inducers | rifampin, carbamazepine, phenytoin, apalutamide, St John's wort, enzalutamide, mitotane | |
| Medications that prolong QT interval | Class 1A antiarrhythmics : quinidine, procainamide, disopyramide; | |
| | Class 3 antiarrhythmics: amiodarone, sotalol, dofetilide | |
| | Antipsychotics: ziprasidone, chlorpromazine, thioridazine, haloperidol | |
| | Antibiotics: moxifloxacin, ciprofloxacin, erythromycin, ketoconazole | |
| H ₁ receptor antagonists | pheniramine maleate, diphenhydramine, promethazine (antihistamines) imipramine, clomipramine, mirtazapine (tri or tetracyclic antidepressants | |

CYP = cytochrome P450

Appendix D. EPWORTH SLEEPINESS SCALE FOR CHILDREN AND ADOLESCENTS (ESS-CHAD [PARENT/CAREGIVER VERSION])

Appendix E. CAREGIVER GLOBAL IMPRESSIONS OF SEVERITY (CaGI-S) FOR EXCESSIVE DAYTIME SLEEPINESS

Please choose the response below that best describes your child's (care recipient's) likelihood of falling asleep during daytime activities over the past week:

- \Box 0 = Not at all
- \Box 1 = Slight likelihood
- \square 2 = Moderate likelihood
- \square 3 = High likelihood
- \Box 4 = Very high likelihood

APPENDIX F. CLINICAL GLOBAL IMPRESSION OF SEVERITY OF OVERALL CLINICAL STATUS

| Considering your total clinical | experience with th | iis particular population | on, please rate the |
|----------------------------------|--------------------|---------------------------|---------------------|
| patient's condition at this time | . Check one: | | |

| $\Box 1 = Normal$ |
|---------------------------------|
| \Box 2 = Mildly symptomatic |
| □ 3 = Moderately symptomatic |
| \Box 4 = Severely symptomatic |

APPENDIX G. ABERRANT BEHAVIOR CHECKLIST-COMMUNITY, SECOND EDITION (ABC-C)

APPENDIX H. MONTEFIORE-EINSTEIN RIGIDITY SCALE – REVISED FOR RESEARCH STUDIES IN PWS (MERS-R-PWS)

APPENDIX I. 22-ITEM ZARIT BURDEN INTERVIEW (ZBI-22)

APPENDIX J. HYPERPHAGIA QUESTIONNAIRE FOR CLINICAL TRIALS (HQ-CT)

Source: McCandless SE, Yanovski JA, Mille J, et al. Effects of MetAP2 inhibition on hyperphagia and body weight in Prader-Willi syndrome: a randomized, double-blind, placebo-controlled trial. Diabetes Obes Metab. 2017; 19(12):1751-61.

APPENDIX K. FOOD SAFE ZONE QUESTIONNAIRE (FSZQ)

Appendix L. COLUMBIA-SUICIDE SEVERITY RATING SCALE (C-SSRS) VERY YOUNG CHILD/COGNITIVELY IMPAIRED-LIFETIME RECENT

APPENDIX M. COLUMBIA-SUICIDE SEVERITY RATING SCALE (C-SSRS) VERY YOUNG CHILD/COGNITIVELY IMPAIRED-SINCE LAST CONTACT

APPENDIX N. ANXIETY, DEPRESSION, AND MOOD SCALE (ADAMS)

4.0 Purpose

The statistical analysis plan (SAP) describes the statistical methods to be used during the reporting and analyses of data collected under Harmony Biosciences, LLC Protocol HBS-101-CL-002.

5.0 Scope

The SAP outlines the:

- Study Objectives
- Study Design
- Endpoints
- Applicable Study Definitions
- Statistical Methods

6.0 Introduction

This SAP should be read in conjunction with the study protocol Amendment 5, Version 6.0 (dated 13 December 2021) and case report form (CRF) Version 4.0 (dated 28 April 2022). Any further changes to the protocol or CRF may necessitate updates to the SAP.

Final approval of the SAP by Harmony Biosciences and by PRA will occur prior to unblinding the Double-Blind Treatment Phase of the study.

6.1 Changes from Protocol

- The Intent-to-Treat Population is renamed as modified Intent-to-Treat (mITT) Population, but the definition remains the same.
- The Pharmacokinetics (PK) Population was revised to include all patients who have at least one non-missing concentration for either analyte. This new definition of the PK Population means that all PK concentrations will be summarized and plotted even for patients with PK concentration available, but for which PK parameters cannot be determined.
- Additional details to resolve convergence issues for the mixed model repeated measures (MMRM) analysis with an unstructured covariance matrix was added.
- For the OLE Phase reporting, all patients will be analyzed under the same treatment group, i.e., patients will not be grouped based on their randomized treatment. During the OLE Phase, patients will undergo a 3-week titration to reach a target dose of 17.8 mg (ages 6 to <12 years), 26.7 mg (ages 12 to <18 years) or 35.6 mg (ages 18 to 65 years) and continue to received pitolisant at that dose (which corresponds to the high pitolisant dose for each age group as defined in the Double-Blind Treatment Phase) unless they were not titrated to the target dose and are receiving a lower dose based on clinical response and/or tolerability; therefore, the randomized treatment group will not influence the results of the OLE Phase.
- Remove the (pooled) site from all inferential models for consistency across analysis/endpoints. Most of the assessments are performed by the caregiver/patient so it is not expected for the site covariate to contribute to the model.

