6.3.1. Epworth Sleepiness Scale for Children and Adolescents (ESS-CHAD); Parent/Caregiver Version

The parent/caregiver version of the ESS-CHAD is an 8-item, 4-point Likert rating scale where parents/caregivers rate their child's/care recipient's likelihood of falling asleep over the past month while engaging in eight different activities: sitting and reading; sitting and watching TV or a video; sitting in a classroom at school during the morning; sitting and riding in a car or bus for approximately half an hour; lying down to rest or nap in the afternoon; sitting and talking to someone; sitting quietly by himself/herself after lunch; sitting and eating a meal. If the patient has not engaged in an activity, the parent/caregiver is asked to imagine how the activity would have affected the patient. Responses are rated on a scale where 0 = 'would never fall asleep', 1 = 'slight chance of falling asleep', 2 = 'moderate chance of falling asleep', and 3 = 'high chance of falling asleep'. A global score, which represents the sum of responses across all eight items, ranges from 0 to 24; higher scores correspond to greater daytime sleepiness. This assessment will be administered at every on-site study visit. The ESS-CHAD (parent/caregiver version) is provided in Appendix D.

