10.0 Analysis Sets

For the Double-Blind Treatment Phase: The safety analyses will be conducted on the safety population. The mITT population will be used for efficacy analysis. The PK population will be used for PK analyses. Patients will be analyzed according to randomized treatment assignment for efficacy assessments and according to actual treatment received for safety assessments. Patients will be analyzed by treatment, active arms pooled, and overall (where appropriate).

For the OLE Phase: The Open-Label safety population will be used. After completion of the 3-week Titration Period, patients will continue to receive pitolisant at a target dose of 17.8 mg (ages 6 to <12 years), 26.7 mg (ages 12 to <18 years), 35.6 mg (ages 18 to 65 years), unless they were not titrated to the target dose and are receiving a lower dose based on clinical response and/or tolerability, so all patients will be analyzed under the total treatment group.

[figure not shown]

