12.4.2 Open-Label Extension Effectiveness Analyses

Actual and change from Baseline results collected in the OLE Phase will be tabulated with summary statistics for continuous outcomes and frequencies and percentages for categorical outcomes. No p-values will be reported for the OLE Phase. Results will be tabulated for the total group. Baseline will be the pre-double-blind-treatment Baseline (identical to that used for the double-blind analyses).

The following endpoints will be summarized for OLE:

- ESS-CHAD score as rated by caregivers/parents
- CaGI-S for EDS
- CGI-S for overall clinical status related to PWS
- Behavior as measured by the ABC-2
- Behavioral and cognitive rigidity as measured by MERS-PWS
- Psychomotor function as measured by the Cogstate Detection test
- Attention as measured by the Cogstate Identification test
- Working memory as measured by the Cogstate One Back test
- Measure of caregiver burden using ZBI-22
- Total score of the HQ-CT in conjunction with the FSZQ
- Cogstate Psychomotor/Attention Composite Score
- Cogstate Psychomotor/Attention/Working Memory Composite Score

The following endpoints will only be collected for the first year of the OLE study (i.e., at Visit 6 [Month 4], Visit 7 [Month 6], Visit 8 [Month 9] and Visit 9 [Month 12]):

- Behavior as measured by the ABC-2
- Behavioral and cognitive rigidity as measured by MERS-PWS
- Psychomotor function as measured by the Cogstate Detection test
- Attention as measured by the Cogstate Identification test
- Working memory as measured by the Cogstate One Back test
- Measure of caregiver burden using ZBI-22
- Total score of the HQ-CT in conjunction with the FSZQ
- Cogstate Psychomotor/Attention Composite Score
- Cogstate Psychomotor/Attention/Working Memory Composite Score

The following endpoints will be collected until the end of the study:

- ESS-CHAD score as rated by caregivers/parents
- CaGI-S for EDS
- CGI-S for overall clinical status related to PWS

In addition, the same categorical summaries provided for the Double-Blind Treatment Phase will be provided for:

- ESS-CHAD score as rated by caregivers/parents
- CaGI-S for EDS
- CGI-S for overall clinical status related to PWS

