12.6 Safety Analyses

All safety analyses will be completed for the Double-Blind safety and Open-Label safety populations. All safety data will be listed and summarized. No formal statistics will be performed for the safety analysis.

For the Double-Blind Treatment Phase, summaries will be presented by treatment arms and active arms pooled; for the OLE Phase, results will be tabulated for the overall group.

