12.6.1 Adverse Events

An AE is defined as any untoward medical occurrence associated with the use of a drug in humans, whether or not considered drug related.

A TEAE is defined as any event not present before exposure to study drug or any event already present that worsens in intensity or frequency after exposure and up to 30 days after the last dose of study drug. For the OLE Phase, any AE starting on or after the first dose of OLE treatment will be considered treatment emergent.

A serious AE (SAE) is defined as any AE that results in any of the following outcomes: death, is life-threatening, results in inpatient hospitalization or prolongation of existing hospitalization, results in a persistent or significant incapacity or substantial disruption of the ability to conduct normal activities of daily living, or is a congenital anomaly/birth defect. Important medical events that may not result in death, be life-threatening, or require hospitalization may be considered SAEs when, based upon appropriate medical judgment, they may jeopardize the patient and may require medical or surgical intervention to prevent one of the outcomes listed in this definition.

The AE's relationship to study treatment will be evaluated by the investigator. The following relationships will be collected in eCRF: definitely related, probably related, possibly related,

unlikely related, or not related. The AEs that are evaluated as definitely, probably, or possibly related (or with missing relationship) will be considered treatment-related AEs for summary purposes.

The severity of AEs will be classified by the investigator as mild, moderate, or severe. If the severity is missing, the AE will be assumed to be severe.

An overall AE summary will be generated presenting the frequency and percentage of patients and the number of AEs for the following categories. This overall summary will also be provided for each age groups (6 to <12 years; 12 to <18 years and 18 years or older) for the Double-Blind Treatment Phase. The same summary may be repeated for the OLE Phase.

- Any TEAE
- Any treatment-related TEAE
- Any severe TEAE
- Any treatment-related severe TEAE
- Any serious TEAE
- Any treatment-related serious TEAE
- Any TEAE leading to study discontinuation
- Any TEAE leading to discontinuation of investigational product (IP)
- Any TEAE leading to discontinuation of IP and leading to study discontinuation
- Any TEAE leading to interruption of IP
- Any TEAE leading to death

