For patients who opt to continue in the OLE Phase of the study, only AEs starting strictly before the first dose in the OLE Phase will be summarized for the Double-Blind Treatment Phase, and any AEs that started on or after the first dose of treatment in the OLE Phase and up to 30 days after the last dose of treatment in the Double-Blind Treatment Phase will be included in a separate listing (for the OLE Phase reporting); these AEs will be included in the OLE Phase summaries. A listing of all the AEs that were ongoing (i.e. that are ongoing or have a stop date after the first dose of treatment in the OLE Phase) at the end of the Double-Blind Treatment Phase will be included in the OLE Phase reporting to capture additional information for those AEs (such as end date and potential treatments) and patients will not necessarily be on the same treatment as what they were randomized to in the Double-Blind Treatment Phase.

For the OLE Phase, the same data summaries and listings will be produced. The data will be tabulated for overall and by period

. Calculations for AE start and stop dates are detailed in Appendix 5.

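### A shared open-label target dose does not make the former randomised arm irrelevant: pooled early OLE results mix patients at first exposure to study pitolisant with patients on continued exposure

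*SAP*

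**What the plan says.** SAP 6.1 lists OLE pooling as a change from the protocol: "patients will not be grouped based on their randomized treatment". The reason given is that every patient is titrated to the same age-based target dose, apart from those kept lower for response or tolerability; "therefore, the randomized treatment group will not influence the results of the OLE Phase".

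The rule is applied throughout the SAP:
- Analysis sets (SAP 10.0): "so all patients will be analyzed under the total treatment group".
- Effectiveness (SAP 12.4.2): "Results will be tabulated for the total group".
- Safety (SAP 12.6): "for the OLE Phase, results will be tabulated for the overall group".
- Adverse events (SAP 12.6.1): "The data will be tabulated for overall and by period". The definition of the periods is not visible in the public copy.

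For the OLE, SAP 12.6.1 also states that "any AE starting on or after the first dose of OLE treatment will be considered treatment emergent". By contrast, Protocol 9.1 has safety and efficacy endpoints summarised by treatment group and with the active groups pooled.

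**The concern.** The SAP argues from the dose that patients reach to the conclusion that their earlier arm cannot matter. Prior exposure is a separate matter. Protocol 1.2 admits patients to the OLE whatever their double-blind assignment. Former placebo patients therefore take their first study pitolisant on Day 78, former lower-dose patients move to a target above the dose they were on, and former higher-dose patients are re-titrated to a dose they have already taken.

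Two early OLE summaries are affected. The pooled Visit 6 change averages patients about three weeks into treatment with patients about fourteen weeks into it. The pooled early AE rate counts first-exposure events from former placebo patients, whereas the first-exposure events of former pitolisant patients were already counted in the double-blind phase. Long-term safety and effectiveness is a stated secondary objective (SAP 7.2), and these tables are meant to serve it.

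**Working it through.** **The plan's own figure.** Protocol 9.2 gives 80% power for a 3.9-point ESS-CHAD difference between pooled pitolisant (n = 40) and placebo (n = 20) at SD 5. I assume two-sided alpha 0.05.
- SE = 5 × √(1/20 + 1/40) = 1.37, and 3.9/1.37 = 2.85.
- Power is 81.3% by the normal approximation and 80.0% by the noncentral t with 58 df.
- The 95% half-widths, 1.96 × SD × √(1/20 + 1/40), are 2.68 (SD 5) and 3.22 (SD 6), matching the stated 2.7 and 3.2.

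The figure reproduces. It is not in dispute and serves below only as an effect size.

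**Exposure at Visit 6.** Inputs are from Protocol 3.1.4 and Table 8: first open-label dose on Day 78, target dose from Day 92, Visit 6 on Day 99 (±3 days).

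| | Through Day 98 | Including Day 99 |
|---|---|---|
| Former placebo: days on study pitolisant | 98 − 78 + 1 = 21 | 22 |
| of which at target dose | 98 − 92 + 1 = 7 | 8 |
| Former pitolisant: days on study pitolisant | 98 | 99 |

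**ESS-CHAD recall.** Protocol 6.3.1 asks about the "likelihood of falling asleep over the past month". Taking a month as 30 days (an assumption), the window is Days 69 to 98 or Days 70 to 99. For a former placebo patient, 9 or 8 of those days precede Day 78.

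**Share.** Allocation is 1:1:1, so former placebo patients make up w = 1/3 of the OLE if entry is similar across arms. No entry rate is given, so w = 0.2 and 0.5 are also shown.

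**Effect on the pooled Visit 6 mean.** Let former placebo patients have reached a fraction f of a 3.9-point effect, and treat both former pitolisant arms as continued exposure. The pooled improvement then falls short of the continued-exposure improvement by w × (1 − f) × 3.9.
- w = 1/3: 1.30 points (f = 0), 0.65 (f = 0.5), 0.32 (f = 0.75), 0 (f = 1).
- w = 0.2: 0.78 down to 0.
- w = 0.5: 1.95 down to 0.

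**Effect on an AE rate.** Pooled rate = w × p + (1 − w) × r × p, where p is the first-exposure rate and r the ratio of the continued-exposure rate to it. Protocol 1.4 gives headache at 13.5% in pitolisant-treated Phase 2/3 patients; using that as p is an assumption. At w = 1/3 the pooled rate is 6.75% (r = 0.25), 9.0% (r = 0.5) or 13.5% (r = 1). The last value shows no dilution.

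**The case against.** The OLE is descriptive, with no p-values, so no test or error rate is affected. All patients re-titrate from a starting dose, which narrows the difference between former arms, and the difference should fade by Visits 7 to 9 (Days 189 to 369). Protocol 9.4.2.2 leaves OLE detail to the SAP. All of this stands, and it limits the weight of the point.

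Nor is former arm wholly absent from OLE reporting. SAP 12.3.2 can be read as giving OLE exposure by double-blind treatment, and SAP 12.0 displays listings by arm. SAP 12.6.1 adds a separate listing of AEs that start in the OLE within 30 days of the last double-blind dose; with a last dose on Day 77 this runs to Day 107 and so covers titration. The AE split by period may separate early from late events. None of these is an effectiveness or AE summary by former arm.

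Four stronger readings are tempting but unsupported:
- A reader might call former placebo patients drug-naive. No eligibility criterion excludes earlier pitolisant use; only the absence of prior study pitolisant can be claimed.
- A reader might infer that the pre-double-blind baseline loads placebo response onto former placebo patients alone. Change from that baseline contains non-specific response in every arm, and the protocol synopsis itself sets this baseline.
- A reader might fault the SAP for pooling across the Amendment 6 dosing change. This SAP is tied to Amendment 5 and says that later protocol changes may require an update.
- A reader might treat the former placebo patients' change after Day 77 as an estimate of drug effect. It is open-label and uncontrolled; the randomised phase is what estimates the effect.

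**Conclusion.** The inference in SAP 6.1 fails, and it is the only reason given for a departure that the SAP itself lists as a change from the protocol. The exposure gap at Visit 6, about 3 weeks against about 14, follows directly from the dosing schedule. Its consequence for the results is not known. Under a one-third share and a 3.9-point effect, the pooled mean understates the continued-exposure mean by anything from 0 to 1.3 points, and the headache illustration likewise includes no dilution at one end. Those sizes rest on assumed fractions, an assumed share and a 30-day month. The problem concerns how Visit 6 and titration-period summaries are interpreted; it does not show that the later OLE results are misleading. It merits correction because the remedy is specific and cheap.

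**What to change.** Delete the statement in SAP 6.1 that randomised group will not influence OLE results. In the end-of-OLE report, show ESS-CHAD, CaGI-S, CGI-S and treatment-emergent AE summaries by former arm (placebo, lower dose, higher dose) plus total, at least for Visit 6 and the OLE titration period. For former placebo patients, also show change from Visit 5. Make the same edit in SAP 10.0, 12.4.2 and 12.6.

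Protocol 4.3 keeps patients, sites and study personnel blinded to former arm during the OLE, so any by-arm output before the final OLE report must respect that blind.

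The cost is extra columns in descriptive tables from data already collected. The downside is small groups, about 20 patients or fewer per column, so the columns should be read descriptively.
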